## 1.0 Introduction

Racial differences in the burden of lung cancer persist despite significant nationwide efforts to promote smoking cessation. A higher incidence of lung cancer is notable among African American (AA) in comparison to Whites, and this has not changed for more than a decade. Despite the fact that AAs smoke fewer cigarettes per day than Whites, they are less likely to stop smoking and are more likely to engage in deeper and longer inhalations. Although access to health care and other systemic and socio-economic barriers contribute substantially to these problems, biological factors continue to be a critical contributor to lung cancer disparities. In particular, research by the study investigators and others (see also preliminary work section) have raised the intriguing possibility that differences between AA and Whites may be attributable to genetic factors that may contribute to poorer metabolism of tobacco-related carcinogens and increased risk of addiction.

## 2.0 Objectives

Aim 1: Identify ancestry-informative variants in tobacco metabolism and detoxification pathway genes that correlate with metabolic/detoxification capacity in AA smokers.

Aim 2: Identify ancestry-informative variants in tobacco addiction pathway genes that correlate with measures of nicotine dependence in AA smokers.

Aim 3: Explore the possibility that genetic feedback about increased lung cancer risk associated with African American ancestry may influence perceived risk, cancer worry, acute psychological distress, and motivation to quit.

## 3.0 Background/Rationale

*Genetics, race, tobacco-related carcinogen metabolism, and addiction.* Two prominent groups of potent tobacco carcinogens are benzo[a]pyrene and tobacco-specific nitrosamines such as N'-nitrosonornicotine (NNN) and 4-(methylnitrosamino)-1-(3-pyridyl)-1-butanone (NNK). NNK is reduced in the body to NNAL and activated by Phase I enzymes to a reactive metabolite that alkylates DNA or is further detoxified by Phase II enzymes in the *UGT* pathway to NNAL – glucuronide (NNAL-Gluc). Phase III enzymes (ABC transporters) are known to efflux Phase II conjugates from cells to enable excretion from the body. NNAL is a potent carcinogen in rats. Studies demonstrate that urinary NNAL-Gluc:NNAL ratio, a measure of an individual's metabolism and detoxification capacity, is higher in Whites compared to AA, suggesting racial differences in metabolic activation/detoxification of tobacco smoke carcinogens. Genetic polymorphisms have been described for a number of Phase I, II/III enzymes involved in the metabolism of tobacco and efflux of carcinogens. Many of these polymorphisms have been linked to phenotypic differences in protein activity or expression and are likely to be a major source of inter-individual variation in susceptibility to tobacco carcinogenesis and thus increased lung cancer risk. Levels of urinary NNAL metabolites can be influenced by polymorphisms in the Phase I and II genes, highlighting the importance of genetic variants in tobacco metabolism and carcinogenesis.

Interestingly, the association of genetic variants in Phase I/II/III genes with the metabolism and efflux of tobacco smoke carcinogens from cells may prove to be dependent on race, because the frequency of these polymorphisms varies among racial/ethnic groups. Our preliminary data presented below also provides further support by demonstrating that in Phase I/II/III genes,

polymorphisms with varied frequencies between AA and Whites (i.e., Ancestry Informative Markers [AIMs]) are predicted to be biologically important and could influence the expression and function of these genes. Less well studied are ancestry informative polymorphisms related to addiction. Although a number of studies have identified associations between a variety of genetic polymorphisms and addiction and smoking-related outcomes, no study to date has specifically investigated effects of ancestry-informative markers on addiction and smoking behavior in AA smokers.

*Clinical relevance of genetic risk information.* One potentially important clinical application of genetic testing for lung cancer risk is the provision of test feedback to smokers in the hopes of encouraging cessation. Accumulating research in this area has yielded mixed results, with recent meta-analyses suggesting that genetic feedback about increased lung cancer risk can result in significant short-term improvements in smoking cessation, but no long-term changes. These findings are perhaps not surprising, given the poor long-term smoking cessation success rates, even with available treatments. Experimental studies that systematically manipulate risk information and assess immediate outcomes that are relevant to behaviour change (e.g., worry, perceived risk, motivation to quit) might provide a clearer and more accurate picture of the utility of genetic testing feedback in presenting a “teachable moment” in which to intervene to encourage behaviour change. Consistent with this possibility, Consultant [name] and colleagues conducted an experimental study in which hypothetical lung cancer genetic risk information was manipulated, and they found that high-risk information caused immediate increases in motivation to quit smoking. Our pilot data from AA current smokers also confirms this. Similarly, other experimental studies using hypothetical risk information as a model found that genetic risk feedback resulted in immediate increases in worry and perceived risk. Overall, the literature suggests that experimental studies of hypothetical risk can be a useful tool in understanding the short-term effects of receiving genetic risk information. What has not yet been examined is the possibility that adding personally relevant information to the feedback can enhance effects. Feedback regarding genetic ancestry may thus also have a significant impact on perceived risk, worry, and motivation to quit. Based on empirical and theoretical models of health literacy and numeracy advanced by Consultant [name] and others, the proposed study will explore the potentially important contribution of personally relevant quantitative information to key motivational outcomes related to behaviour change. For example, AA smokers who are informed that their genetic ancestry is in fact highly concordant with AA heritage may be particularly concerned about genetic risks that have been shown to be overrepresented in AAs. Conversely, those who learn that they have low levels of genetic concordance with AA heritage may then self-identify less strongly as AA, resulting in lower concern for genetic risks that are overrepresented in AA smokers. To date, no study has investigated this intriguing possibility.

## 4.0 Study Design

This is a multi-centered study being conducted at the following centers:

Fox Chase Cancer Center (FCCC) by the lead investigator, [name], MPH. FCCC will serve as the coordinating center for this study.

CUNY Hunter College under the direction of [name], MPH will conduct community based research initiatives and recruit study participants from the community.

Icahn School of Medicine at Mount Sinai with [name] will obtain IRB approval, recruit subjects and execute the protocol at Mount Sinai.

We will enroll 360 AA smokers, 180 from clinic-based settings in Philadelphia and NYC that serve smokers and 180 from the general community in Philadelphia and NYC. This recruitment strategy will provide a regionally-diverse sample with an increased range of smoking and dependence levels, which will enhance generalizability, as well as power to detect hypothesized genetic effects. To ensure that the demographics of both clinic and community-based samples are balanced, both subgroups will be matched on age and gender.

Subjects that had participated in protocol 14-814, PI [name]'s cohort of cancer-free individuals and indicated they would like to be contacted for possible participation in future research will be offered an opportunity to enroll in this study. These participants will complete the intervention aspect of the study and we anticipate they will help us to reach our recruitment goals. This protocol enrolled subjects in NYC and Philadelphia. It also allowed those enrolled to be notified of other cancer related studies led by [name] and/or her collaborators.

Recruitment and study setting: Philadelphia and NYC are racially diverse, with AAs comprising a large portion of the general populations. This proposed study will leverage on our existing cohort (CAP3) infrastructure, as well as the considerable resources of the Mount Sinai Health System, with which we have partnered to enhance recruitment.

#### *4.1 Subject Recruitment and Data Collection*

**Face-to-face:** As previously described in IRB 11-880, study subjects will be recruited from various locations throughout the metropolitan area of the aforementioned study cities (for example, stores, shops, community centers, senior centers, health fairs etc.). Based on results from protocol 11-880, we have determined that "on-site" (face-to-face) recruitment from various locations throughout the Philadelphia metropolitan area works best for control recruitment; subsequently, we will use this method as the primary recruitment method for this study. Primary care and specialty clinics within TUHS (e.g. ENT and Pulmonary clinics) to identify current smokers. We will also utilize study flyers (attached in recruitment section) throughout the TUHS with the contact information for study staff. If the individual calls in we will answer any questions and schedule their enrollment during their next appointment at a TUHS clinic.

After informed consent is obtained Mouthwash/Saliva samples will be collected at the completion of the study questionnaire. Participants will be supplied with a 50 mL falcon tube containing 10ml of scope. Participants will be instructed to gargle while tilting to the back of the throat for 30-60 seconds before spitting it back into a separate tube. Participants will be required to have refrained from eating and drinking at least 30 minutes prior to performing the mouthwash rinses. All mouthwash samples will be transported at 4 degrees Celsius (on ice packs) to the laboratory where they will be processed. All samples will be labeled with a unique ID number corresponding to the questionnaire but without personal identifiers. For urine collection, study staff will instruct the participant on how to conduct a clean catch urine sample and the participant will self-collect in nearest rest room.

All participants with a history of cancer screening (e.g. Pap test, breast mammography [females], PSA and/or DRE [males], oral or skin cancer screening, etc.) within the past 12 months will be asked to sign an authorization to request information from another facility. We will use the standard authorization form used by Fox Chase

Cancer Center (FCCC) (attached), which authorizes the research study staff to request cancer screening results from another health care facility/medical provider. The signed authorization form will be sent along with a memo outlining the specific cancer screening result that would be requested. All reports will be de-identified upon receipt and labeled with the participants study ID number. The cancer screening results will be collected in order to confirm self-reported cancer status.

All study materials will be labeled with a unique ID and no PHI. Maintenance of participant confidentiality is discussed in detail within the "Risk to Participants" section of this document.

For Aim 3: Participants recruited through Aims 1 and 2 at each of the two study sites will be randomly assigned to one of four conditions, in a 2 x 2 fully-crossed between-groups factorial design. In one group ("High Risk, High Ancestry [HRHA]"), participants will be asked to consider a hypothetical scenario in which genetic test results reveal that: 1) they carry genotypes that place AA smokers at a particularly high (~50%-80%) risk for the development of lung cancer, and 2) their profile of AIMs reflects a particularly high concordance with AA heritage (~90%). In a second group ("Low Risk, Low Ancestry [LRLA]"), participants will be asked to consider a scenario in which genetic test results reveal that: 1) they are at normal (~7%-10%) risk for the development of lung cancer, and 2) their profile of AIMs reflects a particularly low concordance with AA heritage (~10%). The final two groups will receive "High Risk, Low Ancestry (HRLA)" and "Low Risk, High Ancestry (LRHA)" hypotheticals, respectively. Participants will be block randomized by age and gender to one of four groups following the 2 (Risk) x 2 (Ancestry) design. To increase feasibility, randomization will be conducted independently at all sites. Following randomization, participants will be presented with a brochure describing the nature of two hypothetical genetic tests, one which assesses lifetime risk for the development of lung cancer in AA smokers, and one which characterizes the degree of a participant's genetic concordance with AA ancestry. The brochure will be explained in a standardized fashion to the participants by the graduate student trainees. Participants will then be given the hypothetical feedback according to their randomized condition (HRHA, HRLA, LRHA, LRLA), followed immediately by the post-feedback assessments (see Measures). Participants will then be debriefed, offered a \$30 gift card, and thanked for their participation.

**Intervention Administration:** The intervention will be administered by graduate student trainees. They will be trained to administer the brochure and feedback in a standardized fashion. [name] will train the graduate students in the administration of the hypothetical genetic feedback and the collection of questionnaire data during the post-feedback assessment. The trainees will practice with each other until they achieve proficiency. [name] will also personally observe the first five participant interactions in both NYC and Philadelphia, as well as a random selection of later interactions (n=10) to ensure intervention fidelity. Additional training will be conducted as necessary to ensure fidelity to the intervention.

To address Aim 3, we will administer the following well-established questionnaires, all of which have excellent psychometric properties. The questionnaires are brief, so as not to create undue participant burden. Numeracy, an important predictor of response to risk information, will be assessed using the 7-item Subjective Numeracy scale (SNS), developed by Fagerlin and colleagues. Self-perception of Ancestry Scale (a personal

estimation of the genetic proportion of African ancestors) will be assessed using a measure described and validated by Ruiz-Linares et al.

**Post-Feedback Assessment:** Motivation to quit will be assessed using the Motivation to Quit Smoking Scale (MTSS), which has been found to be a strong predictor of quit attempts. Perceived risk of lung cancer will be assessed using an established face-valid perceived risk scale developed and used by PI [name] in previous work. Cancer worry will be assessed using the well-established 4-item Cancer Worry Scale. Psychological distress will be measured using the BSI-18. For all assessments, participants will be instructed to respond based on how they believe they would feel if they actually received the genetic information that was presented to them.

**Projected Recruitment:** The number of participants that will be enrolled into this study will be 180 for 3 years (approximately 60 patients per year, per site).

Number of subjects per year projected at FCCC	Total number of subjects at FCCC	Number of subjects nationally or internationally (if applicable)	Number of subjects at collaborating institutions (if applicable)
Up to: 60	Up to:180	360	180

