**Aim 2:** For each SNP, nicotine dependence (as determined by high-very high FTND scores: 6-10) will be modeled using genotype after adjusting for smoking dose (pack-years), age and recruitment setting using logistic regression (LR). Sensitivity, specificity and prediction accuracy (along with 95% confidence bounds) will be used to characterize the precision of binary predictions from LR. Multiple linear regression will be used to correlate the proportion of African ancestry with FTND score (low vs. high) after adjusting for smoking dose, age and recruitment setting. All tests will be two-sided and the Benjamini-Hochberg method will be used to account for multiple testing. Secondary outcomes will include cigarettes per day, age at initiation, and intention to quit. To account for the potentially large number of SNPs resulting from this univariate analysis, penalized logistic regression (PLR) will be used to develop a prediction model for nicotine dependence using these SNPs. PLR has been demonstrated to have excellent power to identify covariate effects as well as superior prediction accuracy compared to competing methods like Classification and Regression Trees and Multifactor Dimensionality Reduction. Sensitivity, specificity and prediction accuracy (along with 95% confidence bounds) will be used to characterize the precision of binary predictions from PLR. AUC curves (along with 95% confidence bounds) will be used to characterize the predictive value of models from these methods. A participant whose predictive probability is  $> 0.5$  will be classified as having high nicotine dependence; however, alternative thresholds will also be evaluated in this

analysis. In addition, the performance of each model will be evaluated using leave-one-out cross validation. All computations will be performed using R statistical language and environment.

**Sample Size and Power:** With 180 subjects each in the low-medium (scores 0-5) and high-very high (scores 6-10) nicotine dependence groups, we will have 80% power to detect a difference in the range of 0.14-0.19 (in minor allele frequency between groups in SNPs of interest) at the 0.005 significance level. This calculation assumes a 10-40% minor allele frequency in the low nicotine dependence group.

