**Aim 3:** Variance stabilizing and normalizing transformations will be applied to the data as appropriate. Analysis of variance will be used to identify the individual and interaction effects of factors on each outcome measure. The Benjamini-Hochberg FDR method will be used to adjust for multiple tests involving each factor or interaction across the various outcome measures, and each test with an FDR  $\leq 10\%$  will be considered significant. The primary study analyses will be a 2 (Risk) x 2 (Ancestry) factorial ANOVA. With this statistical approach, we will be able to test for main effects of Risk and Ancestry, as well as Risk x Ancestry interactions. The primary outcome measure will be motivation to quit; perceived risk, cancer worry, and psychological distress will serve as secondary outcomes. In addition to this primary analysis, we will also consider including covariates (e.g., demographics, numeracy, FTND, study site, gender, age) to control for external sources of variation. Finally, we will be able to explore possible moderating effects of these covariates. Although of course, the proposed study is not powered to detect such effects, such exploratory findings may be important when deciding next steps in formally utilizing the results to develop interventions aimed at increasing knowledge of genetic lung cancer risk.

**Sample size and power:** Power computations for this aim are based on the 2 x 2 factorial design described above. With 90 participants per experimental condition (combination of genetic risk and ancestry), we would be able to detect an effect size of 0.685 due to genetic risk or ancestry at a significance level of 0.0125 with 80% power. Similarly, we would be able to detect an effect size of 0.895 due to an interaction between genetic risk and ancestry at a significance level of 0.0125 with 80% power. A significance level of 0.0125 has been used to account for the four outcome measures of interest in this aim and the calculations are based on a standard deviation of 1.37 for motivation to quit smoking from the literature.

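### The primary Aim 3 model for motivation to quit names no pre-feedback measure of quitting motivation, although Aim 2 already calls for intention to quit on the same participants; the loss is precision, not validity

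*Combined protocol and SAP*

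**What the plan says.** Section 13.0, Aim 3, is clear about the outcome and the model: "The primary outcome measure will be motivation to quit", and "The primary study analyses will be a 2 (Risk) x 2 (Ancestry) factorial ANOVA". Adjustment is optional and given by example: "we will also consider including covariates (e.g., demographics, numeracy, FTND, study site, gender, age". No prior measure of motivation or intention to quit is on that list.

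Section 4.1 fixes the timing. The hypothetical feedback is "followed immediately by the post-feedback assessments (see Measures"), and under its Post-Feedback Assessment heading: "Motivation to quit will be assessed using the Motivation to Quit Smoking Scale (MTSS"). The answers are conditional on the scenario: "participants will be instructed to respond based on how they believe they would feel if they actually received the genetic information". No earlier administration of the MTSS is described.

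Section 13.0, Aim 2, also needs a quitting measure: "Secondary outcomes will include cigarettes per day, age at initiation, and intention to quit". It gives neither instrument nor time point. The people are the same, since Section 4.1 says: "Participants recruited through Aims 1 and 2 at each of the two study sites will be randomly assigned to one of four conditions". Section 4.1 also mentions a study questionnaire, but the document does not list its items or place it in order relative to the feedback.

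**The concern.** How ready a smoker is to quit before hearing any feedback is likely to be one of the better predictors of the answer given minutes later. With no such measure in the primary model, stable differences between participants stay in the error term and widen the intervals for Risk, Ancestry and their interaction. The interaction has most at stake, because it is the least precisely estimated of the three. The plan needs a related item for Aim 2 in any case, so the precision is available at almost no cost, but only if the item is asked before feedback. It cannot be recovered for participants already seen.

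The unstated timing also leaves a loose end in Aim 2. If intention to quit were read from the post-feedback MTSS, it would carry the randomised scenario, and the Aim 2 covariates (pack-years, age, clinic or community setting) include no term for condition.

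**Working it through.** **Inputs from Section 13.0, Aim 3:** 90 participants per condition (360 in all), SD 1.37, significance level 0.0125, 80% power, detectable effect 0.685 for one factor and 0.895 for the interaction. **Assumptions:** the test is two-sided (not stated for Aim 3); 1.37 is an unadjusted SD (not stated); r, the correlation between the pre-feedback item and post-feedback motivation, is 0.3, 0.5 or 0.7 (not in the documents).

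**Step 1: the plan's own figures.** Normal approximation, with z(0.99375) + z(0.80) = 2.498 + 0.842 = 3.339.

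- One cell against one cell (90 vs 90): 3.339 x 1.37 x sqrt(2/90) = 0.682; the noncentral F gives 0.685. This is the plan's figure.
- Factorial main effect (180 vs 180): 3.339 x 1.37 x sqrt(2/180) = 0.482. Power at 0.685: 0.685 / (1.37 x sqrt(2/180)) = 4.743; 4.743 - 2.498 = 2.246, giving 98.8%.
- Interaction as a difference of differences: SE = 1.37 x sqrt(4/90) = 0.289; detectable 3.339 x 0.289 = 0.964. Power at 0.895: 0.895 / 0.289 - 2.498 = 0.601, giving 72.6%. The stated 0.895 is close only at one-sided 0.0125, where the result is 0.890 (0.894 by F).

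So 0.685 is not the detectable main effect of the factorial design, and the right starting points are 0.482 and 0.964.

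**Step 2: add a pre-feedback covariate.** Residual SD = 1.37 x sqrt(1 - r²). At r = 0.5 this is 1.37 x 0.866 = 1.186. The main effect is then 3.339 x 1.186 x sqrt(2/180) = 0.418, and interaction power follows from 0.895 / (1.186 x sqrt(4/90)) - 2.498 = 1.080, giving 86%. The last column is 360 x (1 - r²), the number giving the precision of 360 without the covariate.

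| r | Residual SD | Detectable main effect | Power at main effect 0.482 | Detectable interaction | Power at interaction 0.895 | Equivalent N |
|---|---|---|---|---|---|---|
| no covariate | 1.370 | 0.482 | 80% | 0.964 | 73% | 360 |
| 0.3 | 1.307 | 0.460 | 84% | 0.920 | 77% | 328 |
| 0.5 | 1.186 | 0.418 | 91% | 0.835 | 86% | 270 |
| 0.7 | 0.978 | 0.344 | 98.5% | 0.689 | 97% | 184 |

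**Step 3: covariate or change score.** If the pre-feedback measure had the same scale and SD, a change score would have SD 1.37 x sqrt(2(1 - r)) = 1.621, 1.370 or 1.061 at r = 0.3, 0.5 or 0.7. That is worse than no adjustment at 0.3, no gain at 0.5, and worse than the covariate model throughout.

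**The case against.** The strongest reply is that a randomised, post-only, between-groups comparison is a legitimate design, and that Aim 3 is exploratory and asks only for between-arm contrasts. That stands. A reader might infer that the Aim 3 contrasts are biased or that the main effects are underpowered; the design and Step 1 support neither.

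Second, the gain rests on an assumed r. At 0.3 it is under 5% of the SD, and the outcome is an answer to a hypothetical while the earlier item would be an actual answer, so a high r cannot be presumed. Nicotine dependence, numeracy and demographics may also enter the model and take up part of the same variance. All of this stands. It limits the size of the gain but not its direction. The covariate list is by example, so it does not exclude a prior quitting measure; it simply does not commit to one.

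Third, a reader might infer that the Aim 2 outcome is contaminated by the scenario. The document does not show that. The item may well be in the study questionnaire, whose contents are not given, and the other Aim 2 measures have no stated timing either. This is an ambiguity to close.

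Fourth, a reader might want a no-feedback arm, or within-arm change as evidence of which arm moved. Neither follows. The low-risk condition is described as normal risk and serves as the reference for that factor. Change from a real answer to a hypothetical one, with no untreated comparator, would not establish direction.

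Finally, asking about quitting beforehand may pull later answers towards consistency and shrink the contrast. A shrinkage of 1 - sqrt(1 - r²), that is 5%, 13% or 29% at the three values of r, would cancel the gain. This is a fair argument against giving the MTSS twice. It weighs much less against a separate item that Aim 2 needs anyway.

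**Conclusion.** The point holds as a loss of precision that is cheap to avoid. It changes little for a main effect of 0.685. For effects near the true detectable limit and for the interaction it is material unless r is low: the detectable main effect goes from 0.48 to between 0.46 and 0.34, and interaction power at 0.895 from about 73% to between 77% and 97%, for r from 0.3 to 0.7. If the interaction figure was meant as one-sided, its starting power is about 80% and the gain is correspondingly smaller.

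These figures use the plan's 0.0125. The planned analysis controls the false discovery rate at 10%, so absolute power will differ, but the proportional reduction in SD will not. It would be wrong to say that 0.685 itself shrinks as the trial's main-effect limit, because that figure belongs to a 90 vs 90 comparison.

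**What to change.** 1. In Section 4.1, name the Aim 2 intention-to-quit item and state that every participant, including those re-contacted from protocol 14-814, answers it in the study questionnaire before randomisation and feedback.
2. In Section 13.0, Aim 2, state that this value, and not the post-feedback MTSS, is the secondary outcome.
3. In Section 13.0, Aim 3, pre-specify the same value as a fixed covariate in the primary 2 x 2 model for motivation to quit (ANCOVA, not a change score).

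The cost is a few sentences and, if the item is not already in the questionnaire, one short question. The downside is that asking about quitting earlier in the visit may slightly damp responses to the feedback. Using the separate Aim 2 item and not repeating the MTSS keeps this small. The sample size need not change.
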